2.5 Randomization

Sequential screening numbers will be assigned to patients at the time of informed consent signing. As they are enrolled into the study and after eligibility on Day -3 at the earliest and prior to dosing on Day 1 at the latest, patients will be assigned to a unique randomization number which are randomly assigned to treatment according to the specified randomization scheme.

The randomization schedule will be computer-generated before the start of the study.

An Interactive Web Response System (IWRS) will be employed to manage patient and treatment assignments.

Patients will be randomized prior to study drug (EYP001a or placebo and NA) administration on Day 1 in the ratio of approximately 3:1 (37:12) into 2 arms:

- Experimental Arm: EYP001a 200 mg QD + NA daily (37 patients)
- Control Arm: Placebo + NA daily (12 patients)

The ratio will be controlled through block randomization.

Patients will also be stratified per HBeAg status, based on medical history HBeAg value or established during screening, to obtain a balanced randomization to both study arms.

3. STATISTICAL CONSIDERATIONS

Data will be handled and processed per the sponsor's representative (Novotech) Standard Operating Procedures (SOPs), which are written based on the principles of good clinical practice (GCP).

3.1 General Considerations

All data collected on the electronic case report form (eCRF) will be presented in the data listings and will be listed and sorted by treatment arm, participant number and visit, where applicable. All descriptive summaries will be presented by treatment group and nominal visit/time point (where applicable).

Unless otherwise stated, the following methods will be applied:

- Continuous variables: Descriptive statistics will include the number of non-missing values (n), arithmetic mean, standard deviation (SD), median, minimum and maximum values.

The minimum and maximum values will be displayed to the same decimal precision as the source data, the arithmetic mean, SD and median values will be displayed to one more decimal than the source data for the specific variable.

95% Confidence Intervals (CIs), mean differences (among treatments and from baseline) and least-square (LS-Means) values will be displayed to one more decimal than the source data for a specific variable. P-values will be displayed to 3 decimal places.

The appropriate precision for derived variables will be determined based on the precision of the data on which the derivations are based, and statistics will be presented in accordance with the above-mentioned rules.

- Figures based on continuous summary data:
 - X-axis will represent the linear scheduled time expressed as -Day x for screening values and +Day y on treatment values
 - Y-axis will represent the Mean (+/-SD) and be presented as box-plots (median interquartile) parameter value (unit).
- Categorical variables: Descriptive statistics will include counts and percentages per category. The denominator in all percentage calculations will be the number of participants in the relevant analysis population with non-missing data, unless specifically stated otherwise. Percentages will be displayed to one decimal place. Proportions will be displayed to 3 decimal places.

95% Confidence Intervals (CIs), difference in proportions, odds ratio's and other categorical parameters will be displayed to one decimal place for percentages. Proportions will be displayed to 3 decimal places. P-values will be displayed to 3 decimal places.
- Repeat/unscheduled assessments: Only values collected at scheduled study visits/time points will be presented in summary tables. If a repeat assessment was performed, the result from the original assessment will be presented as the result at the specific visit/time point. All collected data will be included in the data listings.
- Assessment windows: All assessments will be included in the data listings and no visit windows will be applied to exclude assessments that were performed outside of the protocol specified procedure windows.
- Result display convention: Results will be center aligned in all summary tables and listings. Participant identifiers visit and parameter labels may be left-aligned if required.
- Date and time display conventions: The following display conventions will be applied in all outputs where dates and/or times are displayed:

Date only: YYYY-MM-DD

Date and time: YYYY-MM-DD HH:MM

If only partial information is available, unknown components of the date or time will be presented as 'NK' (not known), i.e., '2016-NK-NK'. Times will be reported in military time.

- End of Study (EoS) vs Early Termination (ET)

For any analyses based on safety data, efficacy and PD data, EOS and ET assessment will be summarized separately.

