#### 4.6. Stopping Rules

Dosing for a patient will be discontinued for any of the following events:

1. One occurrence of an SAE assessed to be definitely, probably or possibly related to dosing with the study drug.
2. One occurrence of a Grade 4 AE (i.e. life-threatening) assessed to be considered “possibly related” or “probably related” to the study drug
3. One occurrence a Grade 3 rash or higher or acute systemic allergic reaction.
4. Confirmation of any of the study drug discontinuation criteria as described in [Section 8.3](#).
5. Occurrence of any condition that, in the opinion of the Investigator, significantly jeopardizes the wellbeing and safety of the patient and is assessed to be probably related to dosing with the study drug.
6. Clinically significant changes in vital signs or ECGs (such as arrhythmias) assessed to be considered “possibly related” or “probably related” to the study drug (i.e., no alternative explanation likely).
7. Clinically significant changes in the safety laboratory tests assessed to be considered “probably related” to the study drug (i.e., no alternative explanation likely).
8. A subject experiences a breakthrough (defined by quantifiable HBV DNA increase of  $\geq 1 \log_{10}$  HBV DNA copies/mL above LLOQ) the subject should return to the study site for a confirmatory measurement within two weeks, and if virologic breakthrough is confirmed, EYP001a or placebo dosing should be stopped and NA treatment should be continued or modified at the investigator’s discretion.

If two or more patients meet study drug stopping criteria #1, or #3 to #8, recruitment and dosing should be suspended or terminated for the remaining patients, pending the outcome of a DSMC review. The DSMC must review all safety data and provide clearance prior to dosing any additional patients.

If one patient meets study drug stopping criteria #2, recruitment and dosing should be suspended or terminated for the remaining patients, pending the outcome of a DSMC review.

If one patient experiences a Grade 5 common terminology criteria for adverse event (CTCAE) toxicity (based on CTCAE, version 5.0), or if more than 2 patients develop a Grade 3 CTCAE toxicity in the same category, the study will be paused, and safety reports

will be submitted to the DSMC for review and clearance prior to dosing any additional patients.

In other situations, re-initiation of study drug may be considered after consultation with the Medical Monitor.

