2.3.2 Secondary endpoints(s)

Efficacy will be assessed as follows:

- HBsAg responder rate (decrease from baseline ≥ 1.0 on the \log_{10} scale) at Week 16 of treatment and Weeks 20, 28 and 40 of follow up.
- HBsAg responder rate (decrease from baseline ≥ 0.5 on the \log_{10} scale) at Weeks 12 and 16 of treatment and Weeks 20, 28 and 40 of follow up.
- HBsAg loss rate (% patients with HBsAg < Lower Limit of Quantification (LLOQ/TND) at Week 16 of treatment and Weeks 20, 28 and 40 of follow-up.
- HBsAg loss rate (% patients with HBsAg < Lower Limit of Quantification (LLOQ/TD) at Week 16 of treatment and Weeks 20, 28 and 40 of follow-up.
- HBsAg loss rate (Proportion of results that are Target Not Detected versus Target Detected) at Week 16 of treatment and Weeks 20, 28 and 40 of follow-up.
- Relapse rate HBsAg (% patients who became negative [HBsAg < LLOQ], then increased with HBsAg > LLOQ) at Week 16 of treatment period and Weeks 20, 28 and 40 during follow-up period.
- Virologic failure rate (breakthrough) of Hepatitis B virus Deoxyribonucleic Acid (HBV-DNA) (% patients with a confirmed quantifiable HBV DNA increase of $\geq 1\log_{10}$ HBV DNA copies/mL above LLOQ) assessed at Week 16 of treatment period and Weeks 20, 28 and 40 during follow-up period.
- % patients with HBV DNA < Lower Limit of Quantification (LLOQ/TND) at baseline, Week 4, 8, 12 and 16 of treatment and Weeks 20, 28 and 40 of follow-up
- % patients with HBV DNA < Lower Limit of Quantification (LLOQ/TD) at baseline, Week 4, 8, 12 and 16 of treatment and Weeks 20, 28 and 40 of follow-up
- HBV-pgRNA decline ($\Delta \log_{10}$) from Day 1 to Weeks 4, 8, 12, 16 of treatment period and Week 40 of maintenance period.
- HBcrAg decline ($\Delta \log_{10}$) from Day 1 to Weeks 4, 8, 12, 16 of treatment period and Week 40 of maintenance period.
- HBeAg quantification for HBeAg pos patients and changes at Week 16 of treatment and Week 40 of follow-up.
- Fibroscan Vibration Controlled Transient Elastography (VCTE) change from screening value to Weeks 16 and 40 or Early Termination (ET) value.

Safety and Tolerability will be assessed as:

- Treatment-emergent adverse events (TEAEs) (including Serious Adverse Event (SAEs))
- All-cause mortality

- Clinical laboratory tests
- Pruritus assessment (VAS and Q5D)
- Vital signs (blood pressure, heart rate, respiratory rate, and temperature)
- Concomitant medications
- Physical examinations
- 12-lead Electrocardiogram (ECG).

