Please note that for this study, first study drug dosing is considered to occur on Day 1.

- **Breakthrough:** Quantifiable HBV DNA increase of $\geq 1 \log_{10}$ HBV DNA copies/mL above LLOQ.
- **Lower limit of quantification (LLOQ):** HBV DNA results i.e HBsAg < LLOQ will be reported as either <LLOQ/Detected (i.e. LLOQ/TD) or <LLOQ/Target Not Detected (i.e. LLOQ/TND), both are considered LLOQ. HBsAg loss rates will be further subdivided accordingly.

- HBsAg decline: Change from Baseline in HBsAg on the log₁₀ scale. Negative values indicate a decline.
- HBsAg loss: Patients with HBsAg < LLOQ/TND.
- HBsAg responder A: A decrease from baseline ≥ 1.0 on the log₁₀ scale, i.e. a change from baseline of ≤ -1.0 . HBsAg results <LLOQ/Target Not Detected will be reported as 0.015 [$\log_{10}(0.015) = -1.852$] and HBsAg < LLOQ/Target Detected will be reported as midpoint between LLOQ/Target Not Detected and LLOQ/Target Detected, i.e. 0.04IU/mL = $\log_{10}(0.04) = -1.4$. Also, HBsAg above LLOQ will be reported as the raw data is reported.
- HBsAg responder B: A decrease from baseline ≥ 0.5 on the log₁₀ scale, i.e. a change from baseline of ≤ -0.5 . HBsAg results <LLOQ/Target Not Detected will be reported as 0.015 [$\log_{10}(0.015) = -1.852$] and HBsAg < LLOQ/Target Detected will be reported as midpoint between LLOQ/Target Not Detected and LLOQ/Target Detected, i.e. 0.04IU/mL = $\log_{10}(0.04) = -1.4$. Also, HBsAg above LLOQ will be reported as the raw data is reported.
- HBsAg Relapse Rate: Patients who became negative (HBsAg<LLOQ), then increased with HBsAg > LLOQ. HBsAg results <LLOQ/Target Not Detected will be reported as 0.015 [$\log_{10}(0.015) = -1.852$] and HBsAg < LLOQ/Target Detected will be reported as midpoint between LLOQ/Target Not Detected and LLOQ/Target Detected, i.e. 0.04IU/mL = $\log_{10}(0.04) = -1.4$. Also, HBsAg above LLOQ will be reported as the raw data is reported.
- Virologic failure: Patients with a confirmed quantifiable HBV DNA increase of $\geq 1 \log_{10}$ HBV DNA copies/mL above LLOQ. HBV DNA results < LLOQ/Target Not Detected will be reported as 10 [$\log_{10}(10) = 1$] and HBV DNA < LLOQ/Target Detected will be reported as midpoint between LLOQ/Target Not Detected and LLOQ/Target Detected, i.e. 20IU/mL = $\log_{10}(20) = 1.3$. Also, HBV DNA above LLOQ will be reported as the raw data is reported.
- HBV-pgRNA decline: Change from Baseline in HBV-pgRNA on the log₁₀ scale. Negative values indicate a decline.

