Figure 14.3.4.2.11 Boxplot of ALP over Time by Treatment (Safety Set)..... 129

Figure 14.3.4.2.12 Individual GGT over Time (Safety Set)..... 130

Figure 14.3.4.2.13 Individual GGT Change from Baseline (Safety Set)..... 131

Figure 14.3.4.2.14 Boxplot of GGT over Time by Treatment (Safety Set)..... 132

Figure 14.3.4.2.15 Individual Total Bilirubin over Time (Safety Set)..... 133

Figure 14.3.4.2.16 Individual Total Bilirubin Change from Baseline (Safety Set)..... 134

Figure 14.3.4.2.17 Boxplot of Total Bilirubin over Time by Treatment (Safety Set)..... 135

Figure 14.3.4.2.18 Individual Lipid Parameters over Time (Safety Set)..... 136

Figure 14.3.4.2.19 Individual HBV DNA versus ALT at Each Visit (Safety Set)..... 137

Figure 14.3.4.2.20 Individual HBV DNA versus AST at Each Visit (Safety Set)..... 138

GENERAL COMMENTS

- Where a count is 0, the percentage will not be shown (e.g. 0(0.0%) will be displayed as 0)
- Unless otherwise states, parameters will be listed in alphabetical order.
- The minimum and maximum values will be presented to the same number of decimal places as recorded in the electronic Case Report Form (eCRF)
- Mean, SD, and Median will be presented to one more decimal place than the raw data
- Percentages will be rounded to one decimal place, with the denominator being the number of subjects in the relevant population with non-missing data, unless otherwise specified
- Change from Baseline:
Change from Baseline will be calculated as:
Change from Baseline = post baseline value – baseline value
- Unscheduled visits will be excluded from summary tables but included in all by-participant listings.
- **Names and order of Treatment Groups for Table Summaries**
 - Group 1 = EYP001a 200 mg QD + NA daily
 - Group 2 = EYP001a 200 mg QD + NA daily HBeAg+
 - Group 3 = EYP001a 200 mg QD + NA daily HBeAg-
 - Group 4 = Placebo + NA daily
 - Group 5 = Placebo HBeAg+
 - Group 6 = Placebo HBeAg-
 - Group 7 = All HBeAg+
 - Group 8 = All HBeAg-
 - Group 9 = All Study Patients

• **Treatment Display by Page**

Page 1, 3, 5, etc.

EYP001a 200 mg QD + NA daily (N=xx)	= EYP001a 200 mg QD + NA daily HBeAg+ (N=xx)	= EYP001a 200 mg QD + NA daily HBeAg- (N=xx)	Placebo + NA daily (N=xx)
---	--	--	------------------------------

Page 2, 4, 6, etc.

Placebo HBeAg+ (N=xx)	Placebo HBeAg- (N=xx)	All HBeAg+ (N=xx)	All HBeAg- (N=xx)	All Study Patients (N=xx)

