		n (%) [1]	xx (xx.x %)	xx (xx.x %)
		p-value	0.XXX	

Source Listing: 16.2.6.1

p-value is based on the Person Chi-squared Test.

[1] Number of subjects at each visit (Visit n) will be used as the denominator for the calculation of all percentages.

Programming Note:

- Only to present Week 16 and Week 40 will consider multiplicity by a combination of a hierarchical fixed test procedure and a Hochberg procedure to adjust p-value.

Table 14.2.4.2 Summary and Analysis of HBsAg Responder Rate B (ITT Set)

Visit	Category	Statistics	Decrease from Baseline \geq 0.5 on the log10 Scale	
			EYP001a 200 mg QD + NA daily (N=XXX)	Placebo + NA daily (N=XXX)
Week 16	HBsAg Responder	n	xx	xx
		n (%) [1]	xx (xx.x %)	xx (xx.x %)
		p-value	0.XXX	
Week 40		n	xx	xx
		n (%) [1]	xx (xx.x %)	xx (xx.x %)
		p-value	0.XXX	

Source Listing: 16.2.6.1

p-value is based on the Person Chi-squared Test.

[1] Number of subjects at each visit (Visit n) will be used as the denominator for the calculation of all percentages.

Programming Note:

- Only to present Week 16 and Week 40 will consider multiplicity by a combination of a hierarchical fixed test procedure and a Hochberg procedure to adjust p-value.

Table 14.2.5 Summary of HBsAg Relapse Rate (ITT Set)

Visit	Category	Statistics	Group 1 (N=XXX)	etc.	Group x (N=XXX)
Week 16		n	xx	xx	xx
	HBsAg Relapse	n (%) [1]	xx (xx.x %)	xx (xx.x %)	xx (xx.x %)
<Repeat for Week 20, 28, 40>		n	xx	xx	xx
	HBsAg Relapse	n (%) [1]	xx (xx.x %)	xx (xx.x %)	xx (xx.x %)

Source Listing: 16.2.6.1

HBsAg Relapse is defined as patients who became negative [HBsAg < LLOQ], then increased with HBsAg > LLOQ.
 [1] Number of subjects at each visit (Visit n) will be used as the denominator for the calculation of all percentages.

Table 14.2.6 Summary of Virologic Failure Rate of HBV DNA (ITT Set)

Visit	Category	Statistics	Group 1 (N=XXX)	etc.	Group x (N=XXX)
Week 16		n	xx	xx	xx
	Virologic Failure Rate	n (%) [1]	xx (xx.x %)	xx (xx.x %)	xx (xx.x %)
<Repeat for Week 20, 28, 40>		n	xx	xx	xx
	Virologic Failure Rate	n (%) [1]	xx (xx.x %)	xx (xx.x %)	xx (xx.x %)

Source Listing: 16.2.6.2

Virologic Failure Rate of HBV DNA is defined as patients with a confirmed quantifiable HBV DNA increase of $\geq 1\log_{10}$ HBV DNA copies/mL above LLOQ.
 [1] Number of subjects at each visit (Visit n) will be used as the denominator for the calculation of all percentages.

Table 14.2.7 Summary of HBV-pgRNA (ITT Set)

Visit	Group 1 (N=XXX)		etc.		Group x (N=XXX)	

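### The SAP's scheduled-values-only default conflicts with the confirmed virologic failure endpoint, and Table 14.2.6 gives no cumulative count, so the breakthrough rate can be misstated in either direction

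*SAP*

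**What the plan says.** **Definition.** SAP 3.2 begins "Virologic failure: Patients with a confirmed quantifiable HBV DNA increase of" and sets the threshold at one log10 above LLOQ. It does not say which samples may confirm, within what interval, to which visit the event belongs, or what happens when there is no retest.

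**Confirmation.** Under Protocol 4.6, criterion 8, after a first rise "the subject should return to the study site for a confirmatory measurement within two weeks". Then, "if virologic breakthrough is confirmed, EYP001a or placebo dosing should be stopped", and the NA may be continued or modified.

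**Which values reach the tables.** SAP 3.1 says "Only values collected at scheduled study visits/time points will be presented in summary tables" and "If a repeat assessment was performed, the result from the original assessment will be presented as the result at the specific visit/time point". The general comments before the mock shells repeat this: "Unscheduled visits will be excluded from summary tables but included in all by-participant listings". The 3.1 rules are defaults that yield to specific statements. SAP 3.2 makes one for baseline, which does use repeat and unscheduled values. There is no equivalent for virologic failure.

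**When and over whom.** SAP 2.3.2 has the rate "assessed at Week 16 of treatment period and Weeks 20, 28 and 40 during follow-up period". Mock Table 14.2.6 has those four rows with the footnote "Number of subjects at each visit (Visit n) will be used as the denominator for the calculation of all percentages". Protocol 7.1 has HBV DNA drawn at every treatment visit, at Weeks 20, 28 and 40, or at early termination (ET). The secondary objective (Protocol 2.1.2, SAP 2.2.2) concerns breakthrough over the 24 weeks after EYP001a stops.

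**The concern.** An endpoint that depends on a retest sits beside a table rule that leaves retests out. Two programmers could follow this SAP faithfully and report different rates. One would require confirmation, see only scheduled values and find almost nothing confirmed. The other would count the original raised value whatever the retest showed.

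The by-visit layout adds a second gap. A patient with a confirmed breakthrough at Week 6 stops study drug, may have the NA changed, and may be below LLOQ again by Week 16. That patient has no row. One who leaves the study drops out of the denominator as well: SAP 3.1 summarises ET results separately, and Table 14.2.6 has no ET row.

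Table 14.2.6 is the only HBV DNA table in the SAP's table index. It is also marked for the DSMC safety and futility meeting, which is timed to 25 patients reaching Week 12. Its first row is Week 16, so at that meeting patients who have not reached Week 16 have no row.

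**Working it through.** The documents give no expected breakthrough rate, power or sample size for this endpoint, so there is no figure to reproduce. The check compares the visit calendar with the two-week confirmation limit.

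**Inputs.** Visit days and windows are from Protocol 3.1 and Appendix A: treatment visits ±3 days (Week 16 = Day 112), follow-up visits ±7 days (Week 20 = Day 140, Week 28 = Day 196, Week 40 = Day 280). The retest limit of 14 days is from Protocol 4.6.

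**Step 1: gap to the next scheduled sample.**
Shortest gap = (next day − its window) − (this day + its window). Longest gap = (next day + its window) − (this day − its window).

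| Rise first seen at | Next scheduled sample | Shortest gap (days) | Longest gap (days) |
|---|---|---|---|
| Weeks 2 to 14 | two weeks later | e.g. (28−3)−(14+3) = 8 | (28+3)−(14−3) = 20 |
| Week 16 | Week 20 | (140−7)−(112+3) = 18 | (140+7)−(112−3) = 38 |
| Week 20 | Week 28 | (196−7)−(140+7) = 42 | (196+7)−(140−7) = 70 |
| Week 28 | Week 40 | (280−7)−(196+7) = 70 | (280+7)−(196−7) = 98 |
| Week 40 | none | – | – |

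For each of the four tabulated visits, no later scheduled sample falls within 14 days, even at the window extremes. Some sentences in Protocol 6.2.3 still give ±3 days for follow-up visits. On that reading the shortest gap after Week 16 is (140−3)−(112+3) = 22 days, and the conclusion is the same. At Weeks 2 to 14 the next scheduled sample can fall within 14 days, so confirmation there may need no unscheduled value.

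**Step 2: visits without a row.** Post-baseline HBV DNA visits: 8 on treatment (Weeks 2, 4, …, 16) + 3 in follow-up = 11. Tabulated: 4. Without a row: 11 − 4 = 7, all on treatment (Weeks 2 to 14).

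**Step 3: which way the error runs (illustration; the inputs are assumptions).**

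- *Too low.* Suppose 4 of 37 active patients have a confirmed breakthrough, a true rate of 4/37 = 10.8%. Let a share f occur before Week 16 and be re-suppressed by then, with the Week 16 row read as status at that visit. The table captures 4(1−f)/37: 10.8% at f = 0, 8.1% at f = 0.25, 5.4% at f = 0.5 and 0% at f = 1.
- *Too high.* Suppose original values are counted and negative retests ignored. If an unconfirmed rise occurs with probability b at each visit, independently, the chance of being counted at least once over four visits is 1 − (1−b)^4: 2.0% for b = 0.5%, 3.9% for 1% and 7.8% for 2%.

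**Step 4: weight of one patient.** Planned active arm: 1/37 = 2.7 points. SAP 15 reports enrolment suspended after about 25 randomisations. If those were split 3:1, the active arm is about 25 × 3/4 ≈ 19, and 1/19 = 5.3 points.

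**The case against.** A reader might infer three stronger things, and the documents support none of them.

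*That confirmed failure cannot be derived.* The 3.1 rule governs what is presented at a visit. It deletes nothing. SAP 3.1 and 12 keep unscheduled HBV marker values in the listings, so a flag can be built. Some rises at Weeks 2 to 14 are confirmed by the next scheduled sample. It is also arguable that the word confirmed in SAP 3.2 is itself the specific statement that overrides the default. But it names no qualifying values, and the mock-shell comments repeat the exclusion without exception. The conflict stands; impossibility does not.

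*That breakthroughs before Week 16 are never counted.* A rise persisting to Week 16 appears there, and the SAP does not say whether that row is visit status or cumulative. Early events can also be seen in the HBV DNA listing, the box plots and individual plots, and the stopping-rules listing. Two patients meeting criterion 8 bring a DSMC review. Criterion 8 stops study drug, not study participation, so leaving the study is possible but not implied. What stands is that these outputs are not a rate. SAP 2.3.2 also lists the proportion below LLOQ at Weeks 4, 8 and 12, but the index has no table for it.

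*That the rate will be understated.* Step 3 shows both directions.

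Two further points are fair. The four time points are the protocol's own endpoint, so the SAP has not departed from it. The objective covers follow-up only, so an on-treatment count is an addition. Neither answers the confirmation problem, which applies in full at Weeks 20, 28 and 40, nor the lack of a rate over the follow-up period that the objective names.

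**Conclusion.** The concern holds in limited form. The default on scheduled and original values conflicts with an endpoint that, at every tabulated visit, can be confirmed in time only by an unscheduled sample. The by-visit table can miss an early confirmed event that was re-suppressed or whose patient left, and it gives no period rate for the stated objective. The reported rate may be too low or too high, and the documents do not fix which.

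The calendar result assumes that visits are held within their windows. The missed-event result assumes that the Week 16 row is visit status, the natural reading of the shell but not a stated one. The 2.7 points (5.3 if about 25 were randomised 3:1) is the weight of one patient, not an estimate of bias. Severity is modest: Protocol 11.3.3.2 makes the endpoint descriptive, with no test or alpha attached. It should still be corrected, because it is the planned tabular summary of breakthrough on the combination.

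**What to change.** 1. **SAP 3.2.** State that scheduled, repeat, unscheduled and ET HBV DNA values are all used to derive confirmed virologic failure, as an exception to 3.1 and the mock-shell comment. Give the confirmation interval, the visit to which the event is assigned, and the handling of a rise with no retest.
2. **Table 14.2.6.** Add the cumulative number of patients with any confirmed breakthrough from first dose to Week 16 and from Week 16 to Week 40, over ITT patients. Beside each, show the number without evaluable HBV DNA in that period. Without that number, an all-ITT denominator would silently count missing patients as non-failures and pull the rate down. Keep the by-visit rows as supportive.

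The cost is a few sentences, one derived flag and descriptive rows beyond the protocol's listed time points. The data are already collected and listed. The change concerns reporting only and leaves criterion 8 as it is.
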